#### Study duration – per patient

- Up to 16 weeks of screening prior to randomization, including a 6 week washout period for other tricyclic antidepressants (TCAs) or monoamine oxidase inhibitors (MAOI).
- 15 weeks of treatment starting at randomization
- Tapering off study drug by one capsule a week from 15 to 17 weeks after randomization
- One week with no study drug from 17 to 18 weeks after randomization

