### 3.5 Standard treatment recommendations

During the screening period, patients will receive a standardized set of recommendations to include dietary modification, weight loss if needed, and exercise. The patient's medications are reviewed to discontinue drugs that might exacerbate the underlying dysmotility disorder. Dietary modification and use of antiemetics or pain medications as appropriate are the primary management approaches. If symptoms require further treatment during the trial, patients will be instructed to take rescue medications that they would usually take such as ondansetron or promethazine for nausea and vomiting and propoxyphene or propoxyphene with acetaminophen for abdominal pain. These recommendations have been prepared by the GpCRC Steering Committee as standard of care in the management of patients with idiopathic gastroparesis (see Standard Operating Procedures IV: Standards of Care for Patients with Idiopathic Gastroparesis). This will help ensure that the patients in both treatment groups receive standard of care treatment for gastroparesis.

---

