As part of the screening process for the NORIG trial, the gastroparesis patient must have a standardized 4 hour scintigraphic evaluation of gastric emptying using a low fat Egg Beaters meal that is available for review by the study physician as outlined in the Standard Operating Procedures, Part I, section 6.3. This may be repeated as part of standard of care for diagnosis or follow-up as determined by the clinical center investigator during screening. The standard of care gastric emptying scintigraphy may have been obtained at any time within 2 years prior to the registration date. Patients must also have a negative upper endoscopy within the last 2 years, to rule out other potential causes of symptoms such as mechanical obstruction, inflammatory or other structural lesions of the GI tract or non-gastrointestinal causes. Recording of screening data on trial forms may not start until the patient has signed the NORIG trial consent statement. Screening and baseline data collection procedures will include questionnaires, physical examination, various laboratory tests, clinical procedures on patients and review of the patient's medical chart. Data abstracted from a patient's chart may include laboratory, endoscopy, scintigraphy and radiology test results. Prior therapy for gastroparesis will be reviewed, and patients will be asked to stop specific treatments such as tricyclic antidepressants, monoamine oxidase inhibitors, strongly anticholinergic medications, calcium channel blockers, and erythromycin. Narcotic pain medication including fentanyl patches and other rescue medications such as propoxyphene or propoxyphene with acetaminophen may not be used more than 3 days per week.

All participants who sign the consent statement will be registered in the trial database. Each participant who starts screening will be accounted for at the end of screening, as either a screening success (randomization) or a screening failure. A screening failure is defined as a participant who signed the consent form and was registered in the NORIG trial data system, but is found to be ineligible prior to randomization; screening failures include patients who meet medical eligibility criteria but change their mind and do not consent to randomization into the trial. The reason for screening failure will be recorded on the randomization form and keyed in the trial database.

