### 5.3 Randomization visit

Randomization is the act of generating the random study medication assignment from the web-based data management system and is the procedure which defines a patient's enrollment into the trial. Randomization can only occur after eligibility has been fully checked and all data collected at screening visits have been keyed to the trial database. The patient will re-affirm their consent and have their vital signs recorded. Women of child bearing potential must have a negative pregnancy test.

The final task at the randomization visit is the generation of the random treatment assignment. The generation process includes the same electronic check on eligibility that the staff may run prior to the randomization visit. The medication assignment will not be generated unless the check finds that the patient is eligible, and the clinic staff indicates that they want to randomize the patient.

The random treatment assignment will consist of a numbered medication bottle; this number will be unique as well as patient and visit specific. This will correspond to numbered bottles of medication which have been sent to the clinical center's research pharmacy (or clinical coordinator if not using a pharmacy) by the GpCRC Drug Distribution Center. The research pharmacy (or clinical coordinator) will issue the specific numbered bottle to the patient. Each patient's random treatment assignment will be generated for that specific patient and will not be transferable to another patient. Once the assignment has been generated, the patient should be issued the assigned study drug (in person) and instructed about when to take the study drug and monitoring for potential adverse effects. The study drug dispensed at the time of randomization will be either a 10 mg capsule of nortriptyline or a similar looking placebo capsule.

The date of randomization is the start (zero) time for reckoning all follow-up visits (i.e., all follow-up visits are scheduled at specific times measured from the date of randomization). The randomization computer program will generate a personalized appointment schedule for the patient; this schedule will indicate the target date for each follow-up visit, as well as the time window around the target date during which the follow-up visit may be done.

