## 5.5 Standardized questionnaires

Several standardized questionnaires will be administered to patients enrolled in the NORIG trial. Questionnaires will be administered at baseline (prior to randomization) and during follow-up at specified intervals (see Appendix 9.2 for the data collection schedule). The purpose of the

questionnaires is to obtain important information regarding gastroparesis symptoms, side effects, and health-related quality of life.

**Patient Assessment of Upper Gastrointestinal Disorders-Symptoms (PAGI-SYM).** A validated 20 question questionnaire that quantifies symptoms of gastroparesis, dyspepsia, and gastroesophageal reflux disease on a 0 to 5 scale for each symptom^21. The PAGI-SYM includes the 9 question Gastroparesis Cardinal Symptom Index (GCSI) - a validated symptom questionnaire that assesses the symptoms of gastroparesis. The GCSI is based on three subscales (postprandial fullness/early satiety, nausea/vomiting, and bloating). For this study, the total GCSI score, representing the sum of symptom scores of the 9 GCSI symptoms will be used.

**Gastrointestinal Symptom Rating Scale (GSRs)**. A clinical rating scale for gastrointestinal symptoms in patients with irritable bowel syndrome and peptic ulcer disease.

**Beck Depression Inventory**, Second Edition (BDI - II). The BDI-II is a commonly used, reliable 21-item self-report measure designed to assess for depression.

**State Trait Anxiety Inventory**. The STAI is a 40-item self-report measure designed to assess both situational and characterological anxiety. This measure provides two subscale scores (State and Trait) and has been shown to exhibit good reliability and internal consistency.

**Patient Health Questionnaire (PHQ-15)**. The PHQ-15 is a brief, self-report measure of somatization. This test has good internal consistency and reliability.

**Brief Pain Inventory.** (BPI). Developed in 1989 by [name] for rapid assessment of the severity and impact of pain in cancer patients. The BPI has since been translated into more than two dozen languages, and is widely used in both research and clinical settings.

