## 6.2 Outcome measures

### Primary outcome measure:

The primary outcome measure is defined as a decrease from the baseline GCSI score (sum of the 9 individual symptom scores) of at least 50% on any two consecutive follow-up visits during the 15 week treatment period with maximum tolerated study drug dose. A sensitivity analysis will compare cumulative GCSI symptom scores averaged across all follow-up visits to rule out the possibility that an effect present in the primary analysis was due to the GCSI score decreasing 50% on two consecutive visits with smaller improvement or worsening on other follow-up visits.

All patients will be followed for the full 18 weeks after randomization regardless of response or

course of treatment to permit an intention-to-treat primary analysis.

The GCSI total score ranges from 0 to 45 (highest severity) and is calculated as the sum of nine individual symptom scores:

$$\begin{aligned} \text{GCSI} = & \text{Nausea (0-5) +} \\ & \text{Retching (0-5) +} \\ & \text{Vomiting (0-5) +} \\ & \text{Stomach fullness (0-5) +} \\ & \text{Not able to finish a normal sized meal (0-5) +} \\ & \text{Feeling excessively full after meals (0-5) +} \\ & \text{Loss of appetite (0-5) +} \\ & \text{Bloating (0-5) +} \\ & \text{Stomach visibly larger (0-5)} \end{aligned}$$

As noted earlier, a GCSI score of 21 or greater is a requirement for enrollment into the trial. The primary outcome measure is a binary (0, 1) variable, which equals to 1, if a GCSI score reduction of 50% or greater, relative to the baseline score, is observed on at least two consecutive follow-up visits during the 15 weeks of treatment and follow-up.

**Secondary outcome measures** will be defined to address the following areas:

- (1) Symptoms
  - Subscores for the GCSI such as nausea/vomiting, postprandial fullness, bloating
  - Individual symptom scores
  - Global overall relief of symptom questionnaire
  - Clinical global patient impression
- (2) Physiology
  - Satiety test: Volume of Ensure® consumed during satiety testing
  - Electrogastrography: Percent time in EGG dysrhythmias (outside 2.5-3.75 cycles per minute)
  - Side effects to treatment requiring stopping medication

**Subgroup differences** in response to nortriptyline will be addressed:

- (1) Differential response to nortriptyline based on pharmacogenetic analysis of patients
- (2) Differential response to nortriptyline based on blood levels of nortriptyline

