## 9.2 Data collection schedule

Assessment/Procedure	Screening Visits			Follow-up visits Weeks from randomization					
	s1	s2	rz	3	6	9	12	15	18
Consent	X	.	.	.	.	.	.	.	.
Gastric emptying scintigraphy review	X	.	.	.	.	.	.	.	.
Upper endoscopy review	X	.	.	.	.	.	.	.	.
Baseline medical history	X	.	.	.	.	.	.	.	.
PAGI-SYM questionnaire	X	.	.	X	X	X	X	X	X
GSRS questionnaire	X	.	.	X	X	X	X	X	X
SF-36 QOL questionnaire	X	.	.	.	.	X	.	X	.
Beck Depression Inventory-II	X	.	.	X	X	X	X	X	X
State Trait Anxiety Inventory	X	.	.	.	.	X	.	X	.
Brief Pain Inventory	X	.	.	.	.	X	.	X	.
PHQ-15 questionnaire	X	.	.	.	.	X	.	X	.
Electrocardiogram (ECG)	X	.	.	.	.	X	X	.	.
Physical exam	X	.	X	.	.	X	X	X	.
Satiety test with electrogastrography (EGG)	.	X	.	.	.	.	X	.	.
Study drug dispensed	.	.	X	X	X	X	X	.	.
Review of study drug adherence	.	.	.	X	X	X	X	X	X
Follow-up medical history including review of adverse events	.	.	.	X	X	X	X	X	X
Labs	.	.	.	.	.	.	.	.	.
CBC, metabolic and hepatic panel	X	.	.	.	.	.	X	.	.
TSH	X	.	.	.	.	.	.	.	.
Plasma banking	.	X	.	.	.	.	X	X	.
DNA banking	.	X	.	.	.	.	.	.	.
Pregnancy test	X	.	X	.	.	X	X	X	.

**Physical exam:** includes measurement of weight, height, waist and hip circumferences, vital signs (temperature, heart rate, blood pressure) general physical findings

**CBC:** Complete blood count: white blood cell count, red blood cell count, hemoglobin, hematocrit, platelet count

**Metabolic panel:** sodium, potassium, chloride, carbon dioxide, glucose, calcium, magnesium, blood urea nitrogen (BUN), creatinine.

**Hepatic Panel:** albumin, total protein, bilirubin, alkaline phosphatase, alkaline aminotransferase (ALT), aspartate aminotransferase (AST)

**TSH:** Thyroid Stimulating Hormone

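### The only pre-treatment GCSI is scheduled at screening visit 1, between 1 day and 16 weeks before randomization, so a 50% fall from baseline need not be a 50% fall during treatment

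*Protocol*

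**What the plan says.** Section 5.5 of the protocol states that "The PAGI-SYM includes the 9 question Gastroparesis Cardinal Symptom Index (GCSI" items, so the GCSI is available only when the PAGI-SYM is given. The row in Appendix 9.2 reads "PAGI-SYM questionnaire X . . X X X X X X": marked at s1, blank at s2 and randomization, then marked at weeks 3 to 18. Section 5.2 agrees. It lists the PAGI-SYM under screening visit 1 and not under screening visit 2. For the randomization visit, section 5.3 says "The patient will re-affirm their consent and have their vital signs recorded" and adds a pregnancy test, but no symptom questionnaire.

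Section 6.2 defines the primary outcome as "a decrease from the baseline GCSI score (sum of the 9 individual symptom scores) of at least 50% on any two consecutive follow-up visits". The same section recalls that a GCSI of 21 or more is required for enrolment. No section defines baseline as a value taken at or near randomization.

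On what happens between s1 and randomization:

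- Design synopsis, study duration: "Up to 16 weeks of screening prior to randomization, including a 6 week washout period for other tricyclic antidepressants (TCAs) or monoamine oxidase inhibitors (MAOI".
- Section 5.2: "patients will be asked to stop specific treatments such as tricyclic antidepressants, monoamine oxidase inhibitors, strongly anticholinergic medications, calcium channel blockers, and erythromycin".
- Section 3.5: "During the screening period, patients will receive a standardized set of recommendations to include dietary modification, weight loss if needed, and exercise".
- Section 4.4 points the other way on washout. It says the prohibited agents are not to be taken during screening at all.
- Design synopsis, visit schedule: at least one screening visit must fall at least one calendar day before randomization, and screening may last no more than 16 weeks after registration.

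**The concern.** Section 5.3 makes the date of randomization time zero for follow-up, but response is counted from an earlier reading. Between the two, symptoms may change for reasons that have nothing to do with study drug: natural fluctuation, which section 2.2 calls considerable, standard-care advice, or the stopping of a drug that was helping or hurting. A patient who improves before the first dose carries part of the response into the trial, in either arm. A patient who worsens must fall by more than half from the true pre-dose state. Selecting on an s1 score of 21 or more and then using that same score as baseline adds some regression to the mean.

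What is at stake is whether the responder proportions can be read as change during treatment, and whether they still correspond to the 0.30 and 0.60 assumed in section 6.5. An analysis plan cannot repair this later, because no analysis can use a score that was not collected.

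**Working it through.** **1. The plan's own sample size.** Inputs from section 6.5: 0.30 and 0.60, two-sided alpha 0.05, power 90%. With an average proportion of 0.45, the stated formula gives n = [1.960 × √(2 × 0.45 × 0.55) + 1.282 × √(0.30 × 0.70 + 0.60 × 0.40)]² / 0.30² = (1.379 + 0.860)² / 0.09 = 55.7, so 56 per group. This reproduces the protocol's figure. Solving the same formula for power at 65 per group gives 93.9%. The point below does not change the 56.

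**2. The effective threshold.** Let S be the s1 score and R the score at randomization. A responder must reach 0.5 × S, so the fall needed after randomization is 1 − 0.5 × S/R. With S = 30 the target is 15:

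| R at randomization | Change since s1 | Fall needed on treatment |
|---|---|---|
| 21 | −30% | 1 − 15/21 = 28.6% |
| 24 | −20% | 1 − 15/24 = 37.5% |
| 27 | −10% | 1 − 15/27 = 44.4% |
| 30 | 0 | 50.0% |
| 33 | +10% | 1 − 15/33 = 54.5% |
| 36 | +20% | 1 − 15/36 = 58.3% |

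The arithmetic is exact. The size of the change is an assumption, because the documents give none.

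**3. Responder rates and power under assumed drift.** Illustrative simulation; all inputs are assumptions. GCSI mean 28, between-patient SD 6, visit-to-visit SD 3.5, entry at s1 of 21 or more, mean true reductions of 30% on placebo and 50% on active, response on two consecutive of five visits. Drift is the mean change in GCSI points from s1 to randomization. Power uses the section 6.5 formula at 65 per group on these rates, which are rounded to two decimals.

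| Drift | s1 baseline: placebo / active | Difference | Power | Randomization baseline: placebo / active | Difference | Power |
|---|---|---|---|---|---|---|
| −5 | 0.46 / 0.71 | 0.25 | 83.2% | 0.28 / 0.55 | 0.27 | 88.7% |
| 0 | 0.30 / 0.57 | 0.27 | 88.3% | 0.26 / 0.54 | 0.28 | 91.2% |
| +5 | 0.20 / 0.45 | 0.25 | 86.9% | 0.25 / 0.53 | 0.28 | 91.5% |

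The power cost is 5.4, 2.9 and 4.5 points. The placebo rate against s1 moves from 0.20 to 0.46 across the three rows. Against a randomization baseline it stays between 0.25 and 0.28.

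**4. Sensitivity to those assumptions.** A second setting used mean 27, visit SD 4.5, reductions of 20% and 47% with a between-patient SD of 30%, and drift from 10% worsening to 20% improvement. Against s1, the treatment difference stayed between 0.29 and 0.31, while the placebo rate moved from 0.18 to 0.37. The shift in absolute rates therefore appears in both settings; the loss of power does not. With no drift, regression to the mean alone is small: placebo 0.30 against 0.26 in the setting of step 3, and 0.22 against 0.21 when the between-patient SD of the reduction is set at 20%.

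**The case against.** The strongest reply is that the s1 score is fixed before allocation. Drift then falls on both arms alike in expectation, and the primary test in section 6.3 compares arms. That stands. A reader might infer that the stale baseline biases the treatment comparison or inflates type I error; the design gives no support for either.

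A reader might also infer that the baseline is routinely 16 weeks old and taken on a tricyclic. The documents do not say so. Sixteen weeks is a ceiling and one calendar day is the floor. Section 5.1 lets randomization be combined with the last screening visit, and section 5.2 calls the split between screening visits a guideline. Section 3.5 places the advice in the screening period without saying it follows s1. On washout, the synopsis and section 5.2 allow drugs to be stopped after screening starts, while section 4.4 bars them during screening; these passages must be reconciled. What remains is that nothing requires a GCSI near time zero. For a patient who does stop a tricyclic after s1, the six-week rule makes the baseline at least six weeks old.

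A third tempting reading is a serious loss of power. If 20% of would-be non-responders qualified through pre-randomization change alone, the rates would be 0.30 + 0.20 × 0.70 = 0.44 and 0.60 + 0.20 × 0.40 = 0.68, with power of 79.4% at 65 per group. But qualifying with no further fall requires the GCSI to halve before the first dose, and nothing in the documents suggests that for a fifth of patients. Section 6.5 also raised 56 to 65 per group expressly to cover mis-specified response rates.

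**Conclusion.** The point holds as a weakness in measurement, not in validity. As scheduled, one s1 score of variable age serves as both entry value and outcome denominator, and the 50% criterion is a 50% on-treatment fall only for patients who did not change before dosing. That much follows from the schedule and arithmetic.

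The consequence is that absolute responder rates mix pre-randomization change with response during treatment. Power may fall by about 3 to 5 points at 65 per group under an assumed mean drift of 0 to 5 points, or hardly at all under other assumptions. The size and direction of drift, the GCSI variances and the share of patients needing washout are all absent from the documents. It should be fixed because the remedy is cheap and the missing score cannot be recovered once a patient is dosed, not because the trial's comparison is at risk.

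**What to change.** In Appendix 9.2 and section 5.3, add the PAGI-SYM at the randomization visit, after any washout and before the first dose, and before the satiety test if the visits are combined. In section 6.2, define that score as the baseline GCSI for the primary outcome.

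Keep the s1 score for the eligibility threshold of 21 and do not recheck the threshold on the new baseline. Rechecking would select on the baseline itself and bring regression to the mean back: under the assumptions of step 3 with a 5-point fall, the mean upward error in baseline would be about 1.0 point, against about 0.5 for s1 now. The price of not rechecking is that some patients will be below 21 on the day they are randomized.

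Reconcile section 4.4 with the synopsis and section 5.2 on whether washout may take place within screening.

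The cost is one extra 20-item questionnaire at a visit that already takes place, plus an amendment. If patients have already been randomized, section 6.2 must also say which baseline applies to them, since their randomization score does not exist.

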### 9.3 Whole blood draw schedule

Procedure	Study visit (wk)								Total
	s1	s2	3	6	9	12	15	18	
Complete blood count	5	.	.	.	.	5	.	.	10
Metabolic panel	5	.	.	.	.	5	.	.	10
Hepatic panel	5	.	.	.	.	5	.	.	10
Thyroid stimulating hormone	5	.	.	.	.	.	.	.	5
Blood for DNA banking - including pharmacogenomic analysis	.	20	.	.	.	.	.	.	20
Blood for plasma banking - including study drug level measurement	.	10	.	.	.	10	10	.	30
Total (in mL)	20	30	0	0	0	25	10	0	85

**Complete blood count:** white blood cell count, red blood cell count, hemoglobin, hematocrit, platelet count

**Metabolic panel:** sodium, potassium, chloride, carbon dioxide, glucose, calcium, magnesium, blood urea nitrogen (BUN), creatinine

**Hepatic panel:** albumin, total protein, alkaline phosphatase, alkaline aminotransferase (ALT), aspartate aminotransferase (AST), bilirubin

## 9.4 Glossary

---

ALP	- alkaline phosphatase
ALT	- alanine aminotransferase
AST	- aspartate aminotransferase
BMI	- body mass index (kg/m  )
BUN	- blood urea nitrogen
CBC	- complete blood count
CGPI	- Clinical Global Patient Impression question
C-kit	- CD117; a tyrosine kinase receptor type III
CMP	- complete metabolic panel
CPM	- cycles per minute
CTCAE	- Common Terminology Criteria for Adverse Events
CYP	- cytochrome P450 enzyme
CYP2D6	- enzyme that metabolizes nortriptyline; can affect drug levels and efficacy
DCC	- Data Coordinating Center
DSMB	- Data and Safety Monitoring Board
EGG	- electrogastrography
FD	- functional dyspepsia
FDA	- Food and Drug Administration
GE	- gastric emptying
GCSI	- Gastroparesis Cardinal Symptom Index
GpCRC	- Gastroparesis Clinical Research Consortium
GpR	- Gastroparesis Registry
GSRS	- Gastrointestinal Symptom - Rating Scale
HbA1c	- glycosylated hemoglobin A1c
HIPAA	- Health Insurance Portability and Accountability Act
ICC	- interstitial cells of Cajal
IND	- Investigational New Drug application
IRB	- Institutional Review Board
MAOI	- monoamine oxidase inhibitor
MAR	- missing at random
NIDDK	- National Institute of Diabetes and Digestive and Kidney Diseases
NORIG	- N ortriptyline for I diopathic G astroparesis
PAGI-SYM	- Patient Assessment of Upper Gastrointestinal Disorders Symptom Severity Index
po	- by mouth, orally
PHQ-15	- Patient Health Questionnaire on somatization
qhs	- at bedtime
QTc	- QT interval corrected for heart rate; time between start of the Q wave and end of the T wave in the heart's electrical cycle
SAE	- serious adverse event
SOP	- standard operating procedures
SSRI	- selective serotonin reuptake inhibitor
TCA	- tricyclic antidepressant
TSH	- thyroid stimulating hormone
WBC	- white blood cell count

---

